**Table 16: Serum Chemistry Potentially Clinically Significant Criteria (Study RVT-101-2001)**

Parameter	Gender	Low PCS	High PCS
Alanine aminotransferase (U/L)	Male	NA	133
	Female	NA	100
Albumin (g/L)	Male/Female	29	NA
Alkaline phosphatase (U/L)	Male	NA	323
	Female	NA	246
Aspartate aminotransferase (U/L)	Male	NA	118
	Female	NA	103
Direct bilirubin (umol/L)	Male/Female	NA	7.7
Total bilirubin (umol/L)	Male/Female	NA	30.8

Calcium (mmol/L)	Male/Female	1.99	2.91
Creatinine (umol/L)	Male	NA	174
	Female	NA	147
GGT (U/L)	Male	NA	136
	Female	NA	93
Creatinine clearance (mL/min)	Male/Female	29	NA
Random glucose (mmol/L)	Male/Female	2.9	NA
Potassium (mmol/L)	Male/Female	3.4	5.6
Sodium (nmol/L)	Male/Female	129	151

**Table 17: Haematology and Differentials Potentially Clinically Significant Criteria (Study RVT-101-2001)**

Parameter	Gender	Low PCS	High PCS
WBC (10  /L)	Male/Female	2.9	100.1
Hemoglobin (g/L)	Male	99	196
	Female	99	181
Platelets (10  /L)	Male/Female	74	NA
Absolute Neutrophil Count (10  /L)	Male/Female	1.4	NA
Calculated Absolute Neutrophil Count (10  /L)	Male/Female	1.4	NA
Absolute Lymphocyte Count (10  /L)	Male/Female	0.7	5.1
Absolute Lymphocyte Count (10  /L)	Male/Female	0.7	4.1

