## 10.2. Clinical Laboratory

Clinical laboratory parameters will be presented using three methods:

1. Tabulations of observed values over time. Group-mean plots (mean and standard error) over time will also be provided. Reference lines for the upper and lower normal values will be provided: where there are difference reference ranges for males and females, the highest (or lowest) value will be used as the reference line.
2. Tabulations of the incidence of potentially clinically significant (PCS) values by visits and at ANY TIME which includes 7 days after the date of the last dose of double-blind study medication. A focus will be on new-onset PCS values, ie, patients with pre-existing PCS values at pre-treatment will not be considered to have new-onset values on-treatment. For purposes of this analysis, the most extreme (highest and lowest) value AT ANY TIME for a parameter (for a given patient) will be used. Thus, a patient may contribute to both a low PCS value for a parameter as well as a high PCS value for that same parameter. PCS laboratory values are presented for serum chemistry in [Table 16](#) and for hematology in [Table 17](#).
3. Shifts from baseline to on-treatment, where values are categorized as low, normal, or high according to the lab normal values. For purposes of this analysis, the most extreme on-treatment values will be used (most extreme low and most extreme high). Shifts from baseline will be based on laboratory normal ranges as provided by the central laboratory.

In addition, the incidence of OTAEs relating to haematology and to serum chemistry laboratory parameters during the Double-Blind Treatment Period will be presented. These laboratory AEs will be identified from a review of the adverse events and select SOC and PTs will be included.

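### SAP Table 17 lists absolute lymphocyte count twice with different high PCS limits (5.1 and 4.1), so the PCS-high lymphocyte tabulation is not uniquely defined

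*SAP*

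**What the plan says.** SAP section 10.2 plans three laboratory displays: observed values over time, PCS incidence, and shifts from baseline. Table 17 supplies the haematology limits for the second of these: "Tabulations of the incidence of potentially clinically significant (PCS) values by visits and at ANY TIME". For that display, "the most extreme (highest and lowest) value AT ANY TIME for a parameter (for a given patient) will be used". The section puts the focus on new-onset values: a subject who already had a PCS value before treatment is not counted as new-onset.

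Two rows in Table 17 carry the label "Absolute Lymphocyte Count (10 9 /L"). In full they read:

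- "Absolute Lymphocyte Count (10 9 /L) Male/Female 0.7 5.1"
- "Absolute Lymphocyte Count (10 9 /L) Male/Female 0.7 4.1"

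No footnote or text distinguishes them. The neutrophil rows just above also form a pair, but there the second has its own name and repeats the limits of the first: "Calculated Absolute Neutrophil Count (10 9 /L) Male/Female 1.4 NA".

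The shift display works differently: "Shifts from baseline to on-treatment, where values are categorized as low, normal, or high according to the lab normal values", with ranges supplied by the central laboratory. Protocol section 10.4.5.2 separately flags values outside the reference range as H or L.

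**The concern.** One parameter has two high limits, and both cannot be programmed under the same name. The two rows agree in label, unit, sex group and low limit, so a programmer has nothing by which to choose. Printing both would give two lines with the same label and possibly different counts.

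What is at stake is the PCS-high lymphocyte rate by arm, by visit and at any time, together with the new-onset count that the SAP singles out. SAP section 2 says that decisions on the final analyses were made before unblinding. On this parameter the text does not record a decision. If it were settled only once treatment codes were known, the choice of limit could be influenced by the results.

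**Working it through.** No sample size, power or error rate is involved. The check applies the two rows to the same subject and asks where the answers differ.

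**Inputs**

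- High limits 5.1 and 4.1, low limit 0.7 in both rows (SAP Table 17). The high limits are 5.1 − 4.1 = 1.0 × 10^9/L apart.
- New-onset rule: a subject with a PCS value before treatment is not counted as new-onset (SAP 10.2).
- Assumption: a value at or above the limit is flagged. Table 17 has no inequality signs, whereas Table 18 (vital signs) does. The assumption matters only for values exactly at 4.1 or 5.1.

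**Rule.** Let b be the baseline count, m the highest on-treatment count and L the high limit. A subject is PCS-high if m ≥ L, and new-onset PCS-high if b < L ≤ m.

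**Illustrative subjects** (values chosen to show the logic, not trial data)

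| Baseline b | Highest m | Row with 5.1 | Row with 4.1 |
|---|---|---|---|
| 2.0 | 3.5 | not PCS-high | not PCS-high |
| 2.0 | 4.5 | not PCS-high | PCS-high, new-onset |
| 4.5 | 4.8 | not PCS-high | PCS-high, pre-existing |
| 4.5 | 5.5 | PCS-high, new-onset | PCS-high, pre-existing |
| 2.0 | 5.5 | PCS-high, new-onset | PCS-high, new-onset |

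**Where the rows disagree**

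- PCS-high at any time: only when 4.1 ≤ m < 5.1. The 4.1 row always flags at least as many subjects.
- New-onset under 4.1 but not 5.1: b < 4.1 and 4.1 ≤ m < 5.1 (second subject).
- New-onset under 5.1 but not 4.1: 4.1 ≤ b < 5.1 and m ≥ 5.1 (fourth subject).

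The new-onset count under 4.1 minus that under 5.1 is therefore

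N(b < 4.1 and 4.1 ≤ m < 5.1) − N(4.1 ≤ b < 5.1 and m ≥ 5.1),

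which can be positive or negative. Neither limit is the cautious choice for the display that the SAP emphasises.

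**Where they agree.** Values below 4.1 and values of 5.1 or more are classified alike by both rows. Low flags are identical because both rows use 0.7. Shift tables and H/L flags do not use Table 17.

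**Can the documents settle it?** Protocol Table 5 lists lymphocytes once, within the white-cell differential, and names no second lymphocyte parameter. No other passage gives a PCS limit for lymphocytes. The choice cannot be derived from the text.

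**The case against.** The best defence is that the second row was meant as a calculated count, parallel to the second neutrophil row, and lost that word. This is plausible, but the documents do not say it. It would also leave a difference to explain, since the two neutrophil rows share one set of limits and the lymphocyte rows do not. On that reading the row is still mislabelled and needs an edit.

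The second defence is that the effect is small. This stands. SAP section 10 makes the safety analysis descriptive, protocol section 10.4.5.2 excludes inferential statistics for laboratory data, and protocol section 8.3.2.6 ties AE recording of laboratory findings to clinical significance rather than to PCS limits.

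A reader may also be tempted by a stronger reading of the same table. The WBC row is "WBC (10 9 /L) Male/Female 2.9 100.1" and neither neutrophil row has a high limit, so one might infer that 100.1 is an error and that raised white counts go unflagged. The documents do not support either inference:

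- No passage gives another WBC limit. The figure has the same form as 2.9, 4.1 and 5.1, one decimal step past a round number, so a deliberate cut-off above 100 is possible.
- One-sided limits are common in these tables: platelets in Table 17, and albumin, glucose and creatinine clearance in Table 16. A high neutrophil limit would be an added preference, not a correction.
- It is true that a neutrophil-driven rise short of 100.1 gets no high PCS flag in Table 17. But any white count above the laboratory range is still high in the shift tables and flagged H under the protocol.

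**Conclusion.** The lymphocyte conflict holds. Table 17 gives one parameter two high limits, and the PCS-high and new-onset lymphocyte counts depend on which is used. The affected subjects are those whose highest count, or whose baseline, falls between 4.1 and 5.1 × 10^9/L. How many there will be is unknown, because the documents give no lymphocyte distribution.

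The consequence is limited to one line of a descriptive safety display. No efficacy result, sample size or error rate changes. It is nevertheless a contradiction in a threshold that the analysis uses, rather than a missing detail, and should be corrected.

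The conclusion assumes that the row labels in the public SAP are complete as they read. The WBC limit is a question to the sponsor and not part of the finding.

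**What to change.** Before unblinding, trace both lymphocyte rows to the source list of limits. Then either keep one row with one high limit, or give the second row the name of the distinct parameter it is meant to be and say how that parameter is obtained. Match the constant in the program. The documents do not favour either limit, so 4.1 should not be adopted by default as the safer one: a subject going from 4.5 to 5.5 would lose the new-onset flag.

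In the same edit, state whether a value equal to a limit in Table 17 is flagged, and confirm that the WBC high limit of 100.1 is intended. The rule in section 10.2 that one subject may contribute both a low and a high value for a parameter needs no change.

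The cost is one table correction and the matching program constant, with no new data and no change to any other display.

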### 10.3. Vital Signs

Vital sign data (blood pressure [BP], pulse rate, and weight) will be summarized by treatment, visit, and planned time and listed by subject, visit, treatment, planned time and actual date and time. Change from baseline will also be summarized. The incidence of PCS values will be presented, with a focus on new-onset PCS values by visit and at ANY TIME. Orthostatic BP measurements will also be tabulated using the PCS criteria.

PCS ranges for these parameters are provided in [Table 18](#).

**Table 18: List of Potentially Clinically Significant Ranges for Vital Sign Parameters (Study RVT-101-2001)**

Systolic blood pressure:
Low: < 90 and decrease ≥30 mm Hg
High: ≥ 180 and increase ≥ 20 mm Hg
Diastolic blood pressure:
Low: < 50 and decrease ≥20 mm Hg
High: >90 and increase ≥20 mm Hg
Pulse
Low: <50 bpm and Decrease ≥30 bpm
High: >100 and Increase ≥30 bpm

Weight
≥ 10% increase from baseline
≥ 10% decrease from baseline
Orthostatic Hypotension
≥ 30 mmHg decrease (reduction) in SBP upon positional change
≥ 20 mmHg decrease (reduction) in DBP upon positional change

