**Table 19: List of Potentially Clinically Significant Ranges for ECG Parameters (Study RVT-101-2001)**

QTcF Interval
High: >500 msec only
High: Increase ≥ 60 msec only
High: >500 and Increase ≥ 60

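### SAP Table 18 counts a low pulse, SBP or DBP as PCS only when an absolute limit and a large fall are both met, so PCS incidence understates how many subjects cross the stated limits

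*SAP*

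**What the plan says.** SAP 10.3 summarises blood pressure, pulse and weight by treatment and visit, with change from baseline, and presents the incidence of PCS values by visit and at any time, with the focus on new-onset values. Table 18 supplies the criteria. The three low rows are:

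- pulse: "Low: <50 bpm and Decrease ≥30 bpm"
- SBP: "Low: < 90 and decrease ≥30 mm Hg"
- DBP: "Low: < 50 and decrease ≥20 mm Hg"

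The high rows also join a level to a change, for example "High: >100 and Increase ≥30 bpm" for pulse. The weight rows use change alone. So do the orthostatic hypotension rows, such as "≥ 30 mmHg decrease (reduction) in SBP upon positional change".

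SAP 10.2 explains new onset for laboratory values: "patients with pre-existing PCS values at pre-treatment will not be considered to have new-onset values on-treatment".

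For QTcF, Table 19 has three separate rows: the level alone, the change alone ("High: Increase ≥ 60 msec only"), and both together. The laboratory limits in Tables 16 and 17 are levels alone.

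**The concern.** A reader of the PCS table sees a limit of 50 bpm and will take the count as the number of subjects who went below 50. It is not. It is the number who went below 50 and also fell by at least 30. For a subject who starts at 70, the limit in effect is 40.

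Every categorical output for blood pressure and pulse in SAP 10.3 uses the Table 18 criteria, so no other table in that section gives the number of subjects below a level. Vital signs, including orthostatic changes, are a named safety evaluation in the protocol. The repeat dosing at 70 mg described in Protocol 3.3 lasted up to 10 days, while this trial treats for 24 weeks. A PCS count near zero could be taken as evidence that low values did not occur, when it shows only that level and fall rarely coincided.

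**Working it through.** The plan states no expected PCS incidence and no baseline vital signs, so there is no figure of its own to reproduce. I take the decrease as measured from baseline; Table 18 says so for weight but does not spell it out for blood pressure and pulse.

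**Threshold arithmetic (inputs from Table 18).** A whole-number reading v below the limit is flagged only if baseline ≥ v + required fall.

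| Parameter | Limit | Required fall | Highest reading that can be flagged | Lowest baseline for that reading |
|---|---|---|---|---|
| Pulse (bpm) | <50 | ≥30 | 49 | 49 + 30 = 79 |
| SBP (mmHg) | <90 | ≥30 | 89 | 89 + 30 = 119 |
| DBP (mmHg) | <50 | ≥20 | 49 | 49 + 20 = 69 |

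Below those baselines the limit in effect is baseline minus the required fall:

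- Pulse: from 70 it is 70 − 30 = 40; from 60 it is 30.
- SBP: from 110 it is 80.
- DBP: from 60 it is 40.

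Example: 70 to 45 is a fall of 25, so it is not counted. 75 to 45 is a fall of 30, so it is counted.

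**Who could reach a value just under the limit unflagged.** This is the share of subjects with a baseline below 79, 119 or 69. The means and SDs are assumptions. Formula: normal probability with continuity correction, Φ((78.5 − mean)/SD) for pulse, with 118.5 for SBP and 68.5 for DBP.

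- Pulse, mean 65/70/75, SD 10: z = 1.35/0.85/0.35, giving 91%/80%/64%.
- SBP, mean 125/130/135, SD 17: z = −0.38/−0.68/−0.97, giving 35%/25%/17%.
- DBP, mean 70/75/80, SD 10: z = −0.15/−0.65/−1.15, giving 44%/26%/13%.

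**What share of low readings is flagged.** This was simulated with baseline and one later visit as bivariate normal, the same mean and SD at both, rounded to whole numbers, correlation 0.4 to 0.6 and no drug effect. All of these settings are assumptions.

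| Parameter | Assumed mean, SD | Share of readings under the limit that are flagged | Same, among subjects at or above the limit at baseline |
|---|---|---|---|
| Pulse | 66-72, 11 | 1-9% | 1-11% |
| SBP | 125-135, 17 | 17-52% | 23-55% |
| DBP | 70-76, 10 | 11-42% | 15-45% |

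The last column is the relevant one for new onset.

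For scale, at pulse mean 66 and correlation 0.4, 6.67% of readings at a visit are below 50. In an arm of 80 that is 80 × 0.0667 = 5.3 subjects, of whom 5.3 × 0.0552 = 0.3 would be flagged. For SBP at mean 125 and correlation 0.4 the figures are 80 × 0.0183 = 1.5 and 1.5 × 0.3899 = 0.6.

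**Interaction with the new-onset rule.** A baseline value has zero change from itself, so it can never satisfy a level-and-change rule. For these rows the new-onset focus therefore has no baseline PCS value to exclude. It would start to do work in a level-only row.

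**The case against.** The best defence is that the rule is a deliberate choice for specificity. Level and change are joined in all six rows for SBP, DBP and pulse, high and low. The new-onset rule would not screen out a pulse that moves from 51 to 49; the change condition does. The required baseline also falls as the reading becomes more extreme (SBP 80 needs 110, DBP 40 needs 60), so much of what is left out is small crossings. All of this stands, and it is why the combined row should be kept. It does not give the reader the number below the stated limit, and the fall from 70 to 45 is not a small crossing.

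Several stronger readings are tempting, and the documents do not support them:

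- **That the rules cannot flag anything.** Each flags attainable values.
- **That they work only for subjects with a high baseline.** Baselines of 119 systolic and 69 diastolic are ordinary. Under the assumptions above only a minority of subjects lie below them. Only for pulse is it a majority.
- **That bradycardia and hypotension go uncounted in the trial.** SAP 10.3 gives summaries, change from baseline and listings. Protocol 8.3.2.4 sends clinically significant vital signs to adverse events, which SAP 10.1 tabulates. Postural falls have their own change-only rows, and SAP 10.8 covers dizziness, fainting and falls. Investigator ECG interpretation is tabulated as shifts in SAP 10.5. None of these counts subjects below a resting limit, but together they carry the data.
- **That background cholinesterase inhibitors make a low pulse likely.** Nothing in the documents says so, and the point does not rely on it.
- **That sodium abnormalities are missed.** The sodium row of Table 16 reads nmol/L beside potassium and calcium in mmol/L. Taken literally, 140 mmol/L is 1.4 × 10⁸ nmol/L, above the upper limit of 151, so every value would be high and none low. Limits of 129 and 151 are evidently mmol/L figures, the slip may come from text extraction, and the shift tables use laboratory normal ranges rather than Table 16.

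**Conclusion.** The point holds as a limited one about reporting. As written, the low pulse, SBP and DBP rows of Table 18 understate the number of subjects who cross the stated limits, because every flagged subject meets the level condition but not every subject who meets it is flagged. The baselines of 79, 119 and 69 follow from the table by arithmetic, given that the decrease is from baseline. The size does not: the percentages rest on assumed means, SDs and correlations. They support only the ordering, a strong effect for pulse and a smaller one for blood pressure. Expected counts per arm are small in either format. No efficacy conclusion is affected, and the data remain visible elsewhere. This is a cheap improvement to a safety table.

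**What to change.** In Table 18, for SBP, DBP and pulse, keep the combined row and add a level-only row and a change-only row, using the cut-offs already in the SAP. State that change is from baseline, and apply the new-onset rule of SAP 10.2 to each row. This is the layout Table 19 already uses for QTcF. No threshold changes.

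The cost is table wording and 3 parameters × 2 directions × 2 = 12 extra rows (6 if only the low direction is done). The downside is that some small crossings of a limit will be counted, but they will appear in their own row, with the combined row beside it.

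Editorial only: check the sodium unit in Table 16 against the source and align it with potassium and calcium if it does read nmol/L.

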#### 10.4. Physical and Neurological Examinations

Physical and neurological examination data will be listed by patient and time point.

#### 10.5. ECGs

ECG data will be summarized by treatment, visit, and planned time and listed by subject, visit, treatment, planned time and actual date and time. Change from baseline will also be summarized.

The ECG analysis will include a careful review of QTcF values. As part of this review, a summary of the number (percent) of patients with QTcF values in the following ranges will be provided: ≤450 msec, >450 to ≤480 msec, >480 to ≤500 msec, and >500 msec. This will be performed by visit as well as at ANY time during the double-blind treatment period and 7 days after the last dose (where the highest QTcF value will be used for that assessment).

The overall Investigator interpretation of ECG by visit (shifts from baseline) will be tabulated. The incidence of PCS values will be presented, with a focus on new-onset PCS QTcF values (Table 19).

**Table 19: List of Potentially Clinically Significant Ranges for ECG Parameters (Study RVT-101-2001)**

QTcF Interval
High: >500 msec only
High: Increase ≥ 60 msec only
High: >500 and Increase ≥ 60

#### 10.6. Pregnancy

If any female subjects or female partners of male subjects become pregnant during the study, a listing will be provided.

#### 10.7. Suicidality

The following outcomes are C-SSRS categories and have binary responses (yes/no). The categories have been re-ordered from the actual scale to facilitate the definitions of the composite and comparative endpoints, and to enable clarity in the presentation of the results.

- Category 1 – Wish to be Dead

- Category 2 – Non-specific Active Suicidal Thoughts
- Category 3 – Active Suicidal Ideation with Any Methods (Not Plan) without Intent to Act
- Category 4 – Active Suicidal Ideation with Some Intent to Act, without Specific Plan
- Category 5 – Active Suicidal Ideation with Specific Plan and Intent
- Category 6 – Preparatory Acts or Behavior
- Category 7 – Aborted Attempt
- Category 8 – Interrupted Attempt
- Category 9 – Actual Attempt (non-fatal)
- Category 10 – Completed Suicide
- Self-injurious behavior without suicidal intent is also a C-SSRS outcome (although not suicide-related) and has a binary response (yes/no).

Endpoints based on the above categories are defined below.

- **Suicidal ideation:** A “yes” answer at any time during treatment to any one of the five suicidal ideation questions (Categories 1-5) on the C-SSRS.
- **Suicidal behavior:** A “yes” answer at any time during treatment to any one of the five suicidal behavior questions (Categories 6-10) on the C-SSRS.
- **Suicidal ideation or behavior:** A “yes” answer at any time during treatment to any one of the ten suicidal ideation and behavior questions (Categories 1-10) on the C-SSRS.
- Self-injurious behavior without suicidal intent.

A shift table to present changes from pre-treatment to any time post-first-dose will be assessed, with the number (and percent) of subjects showing a worsening from baseline on any of the four endpoints.

The C-SSRS was collected at screening (and the assessment was based on outcomes from the past year), while baseline collection was based on outcomes ‘since the prior visit’. Thus, the analysis will be done in two ways:

1. Shifts from screening, where C-SSRS is relative to patient recall of the past year (using Screening value C-SSRS, and is shifts to each post-screening time point).
2. Shifts from baseline, where C-SSRS is collected relative to patient recall since the PREVIOUS visit, using Baseline value C-SSRS and is shifts to each post-baseline time point).

Table 20 presents the general manner in which these data will be tabulated.

**Table 20: Sample Table Demonstrating How C-SSRS Outcomes will be Presented (Study RVT-101-2001)**

Treatment	Baseline Category	Treatment Category		
		No suicidal ideation or behavior n (%)	Suicidal ideation n (%)	Suicidal behavior n (%)
Drug Name (N=xxx)	No suicidal ideation or behavior	x (%)	x (%)	x (%)
	Suicidal Ideation	x (%)	x (%)	x (%)
	Suicidal Behavior	x (%)	x (%)	x (%)
Comparator Name (N=xxx)	No suicidal ideation or behavior	x (%)	x (%)	x (%)
	Suicidal Ideation	x (%)	x (%)	x (%)
	Suicidal Behavior	x (%)	x (%)	x (%)

Notes: N = number of patients with a baseline and post-baseline C-SSRS assessment, n = number of patients in category. % = 100\*n/N.  
 Baseline refers to [specify definition]  
 Suicidal Ideation includes any one of the five suicidal ideation events (Categories 1-5). Suicidal behavior includes any one of the five suicidal behavior events (Categories 6-10).  
 Each patient is counted in one cell only. Patients with both Suicidal Ideation and Suicidal Behavior are included in the Suicidal Behavior category.

A listing of all C-SSRS data will be provided, while a listing of patients who demonstrated a worsening on any one of the four endpoints will also be provided. These listings will include the Study Day (relative to first dose of double-blind treatment) the C-SSRS was collected.

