### **6.3. Exclusion Criteria**

A subject will not be eligible for inclusion in this study if any of the following criteria apply:

Other Causes for Dementia:

- 1) Atypical clinical features or clinical course of dementia that would lead the investigator to conclude primary symptoms are more likely explained by an alternate dementia diagnosis including, but not limited to, Parkinson's disease dementia, vascular dementia, frontotemporal dementia, or Alzheimer's disease dementia.
- 2) A CT or MRI scan performed within the past 12 months or at Screening that is indicative of any other CNS disorder that, in the opinion of the investigator, could be interpreted as the primary cause of dementia (e.g., cerebrovascular disease [transient ischemic attack, stroke, hemorrhage]; structural or developmental abnormality; epilepsy; infectious, or degenerative or inflammatory/demyelinating CNS conditions) or any other history and/or evidence to suggest the same.
- 3) Evidence of the following disorders where this is thought to be the cause of, or to contribute to the severity of, the subject's dementia: current vitamin B12 deficiency, hypothyroidism, neurosyphilis, HIV dementia, or Korsakoff's encephalopathy.
- 4) Focal findings on the neurological exam (excluding changes attributable to peripheral injury) that are inconsistent with a primary diagnosis of DLB.

Confounding Medical Conditions

- 5) History of schizophrenia, major depressive episode in the past 6 months, or any other significant psychiatric condition such as bipolar affective disorder that in the opinion of the investigator would interfere with participation in the study or could affect performance on outcome measures.
- 6) Significant suicide risk as defined by (1) suicidal ideation as endorsed on items 4 or 5 on the C-SSRS within the past year, at Screening or since the last visit at Baseline or; (2) suicidal behaviors within the past year or; (3) clinical assessment of significant suicidal risk during subject interview.
- 7) History of epilepsy or unexplained seizure in the past 5 years or history of significant head trauma with loss of consciousness in the past 5 years.
- 8) History of malignancy during the 5 years before Screening. History of basal cell carcinoma and melanoma in situ are permitted. History of other cancers currently in a non-active state may be acceptable after review with the Medical Monitor.

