### 8.3.2.7. Assessment of Suicidality

Subjects will be assessed for suicidality before and during the study using the Columbia Suicide Severity Rating Scale (C-SSRS). Subjects considered to be at significant risk will be excluded from the study. The C-SSRS is a brief measure which is designed to assess severity and change of suicidality by integrating both behavior and ideation. It assesses intensity of ideation (a potentially important marker of severity), specifically asking about frequency, duration,

controllability, deterrents, and reasons for the ideation which was most severe during the respectively assessed timeframe. Suicidal behavior is also assessed by asking further questions to categorize the behaviors into actual, interrupted, or aborted attempts; as well as preparatory and non-suicidal self-injurious behavior. The C-SSRS will be completed by a rater trained and certified to administer this scale. Any change in C-SSRS score indicating the presence of suicidality should be evaluated by the investigator for clinical significance to determine continued study eligibility ([Section 6.3](#)) and appropriate clinical actions (including but not limited to a referral to a mental health professional).

Clinically meaningful suicidal ideation, suicidal behavior and completed suicide should be recorded as adverse events.

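### SAP 10.7 pools C-SSRS ideation Categories 1-5, so a move from Category 1-3 to Category 4-5 on treatment registers as no change, and no specified C-SSRS table counts Category 4-5 by arm (minor, safety reporting only)

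*SAP*

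**What the plan says.** SAP 10.7 lists ten ordered C-SSRS categories: 1-5 are ideation and 6-10 are behavior. It then defines four yes/no endpoints: ideation (any of 1-5), behavior (any of 6-10), either of these (any of 1-10), and self-injury without suicidal intent.

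The shift analysis is to be reported "with the number (and percent) of subjects showing a worsening from baseline on any of the four endpoints". It is run twice, once against Screening (recall over the past year) and once as "Shifts from baseline, where C-SSRS is collected relative to patient recall since the PREVIOUS visit".

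Table 20 has three levels per arm (none, ideation, behavior) and places each patient in a single cell. Its footnote says "Suicidal Ideation includes any one of the five suicidal ideation events (Categories 1-5". The SAP describes its status this way: "Table 20 presents the general manner in which these data will be tabulated". Two listings are planned: one of all C-SSRS data, and "a listing of patients who demonstrated a worsening on any one of the four endpoints will also be provided".

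The protocol draws one line inside ideation. Exclusion 6 (section 6.3) bars subjects with "suicidal ideation as endorsed on items 4 or 5 on the C-SSRS within the past year, at Screening or since the last visit at Baseline". Section 10.4.5.4 promises counts of ideation and of behavior, and leaves further summaries to discretion.

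**The concern.** Categories 4 and 5 are the ideation levels with intent to act, and they are the ones the protocol treats as significant suicide risk at entry. In an eligible subject, ideation at a reference assessment can only be Category 1-3, so any Category 4-5 report on treatment is new relative to that reference. The planned shift analysis cannot show this step when the subject already reported milder ideation. It also cannot tell a subject who goes from none to a wish to be dead from one who goes from none to a specific plan with intent.

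Suicidality is a named safety objective. At stake is whether a reader comparing arms can see Category 4-5 ideation in a table without counting it by hand from a listing.

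**Working it through.** The plan gives no figure of its own on this point, so the check applies its rules to each possible transition.

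**Inputs.**
- Levels: none; ideation = Categories 1-5; behavior = Categories 6-10 (SAP 10.7, Table 20).
- Worsening: judged on the four yes/no endpoints (SAP 10.7). The SAP does not define the word. A yes/no endpoint can only worsen from no to yes, so that reading is used.
- Reference ideation in an eligible subject: Categories 1-3 (protocol 6.3, exclusion 6, taking its items 4 and 5 to be SAP Categories 4 and 5).

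**Step 1: moves from Category 1-3 to Category 4-5.** There are 3 reference categories x 2 on-treatment categories = 6 moves. With no behavior or self-injury at either time:

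| Endpoint | Reference | On treatment | Worsened? |
|---|---|---|---|
| Ideation | yes | yes | no |
| Behavior | no | no | no |
| Ideation or behavior | yes | yes | no |
| Self-injury | no | no | no |

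Result: 0 of 6 leave the ideation-to-ideation cell, and 0 of 6 count as worsened. The worsening listing uses the same endpoints, so it misses them too.

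**Step 2: moves from none.** None to Category 1 and none to Category 5 both go from no to yes and share one cell. That cell holds 5 possible moves. The 2 that reach Category 4-5 cannot be told from the other 3.

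**Step 3: the two references.** A subject with ideation at Screening but not at Baseline is flagged in the Baseline shift, though not as Category 4-5. To go unflagged in both shifts, the subject must report Category 1-3 at both references.

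**Step 4: other outputs.**

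| Output | What it shows | Category 4-5 by arm? |
|---|---|---|
| Listing of all C-SSRS data (SAP 10.7) | every response, with Study Day | no, by subject |
| On-treatment AE tables (SAP 10.1) | preferred term, maximum intensity, relatedness, discontinuation | no, not by C-SSRS category |
| Disposition (SAP 8.1) | reasons for discontinuation by arm | no |
| Safety committee review (protocol 8.3.2.2) | content as the committee requests | not specified |
| Further summaries (protocol 10.4.5.4) | discretionary | not specified |

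**Step 5: with the fix.** If reaching Category 4-5 from none or Category 1-3 counts as worsening, 6 of 6 moves in Step 1 register. The added row shows the by-arm count for Steps 1 and 2 together.

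**Step 6: how many subjects.** The documents give no ideation rate, and the transition counts above say nothing about how many people are affected. On assumed rates for one reference assessment, subjects x share with Category 1-3 x share of these who escalate gives:
- 240 x 1% x 5% = 0.12
- 240 x 2% x 10% = 0.48
- 240 x 5% x 20% = 2.4

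These figures are only as good as the assumed rates.

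**The case against.** The strongest reply is that this is a display choice and not an error. The SAP delivers the ideation and behavior counts that the protocol promises, and more. Safety analysis is descriptive, so no test depends on the split. Table 20 is a generic sample. Exclusion 6 is an entry rule, and nothing in either document makes it a reporting threshold. For so few expected subjects, a full listing may be enough.

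Much of that stands. There is no conflict between SAP and protocol. But the endpoint definitions and the worsening rule are plan text, not part of the sample table. They give an uneven result: none to Category 1 is counted and listed as worsened, while Category 1 to Category 5 is not.

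A reader might go further and infer that escalating ideation would be missed, or that subjects are left unprotected. The documents do not support that. Protocol 8.3.2.7 says "Any change in C-SSRS score indicating the presence of suicidality should be evaluated by the investigator for clinical significance to determine continued study eligibility". It adds: "Clinically meaningful suicidal ideation, suicidal behavior and completed suicide should be recorded as adverse events". Protocol 8.3.2.1.1 also has the investigator evaluate worsening on the C-SSRS and, if it is clinically significant, record an associated AE where there is one. The AE is to be the underlying manifestation, not the score change. Such events appear by arm under preferred term and intensity, and the safety committee can obtain treatment codes if it identifies a significant concern. These routes carry the safety function. What they do not supply is a count of Category 4-5 ideation by arm.

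**Conclusion.** The point holds as a minor improvement to safety reporting. Under SAP 10.7 as written, a subject who moves from Category 1-3 to Category 4-5, without new behavior or self-injury, is not shifted, counted or listed as worsened against that reference. No specified C-SSRS table gives Category 4-5 ideation by arm.

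This rests on three assumptions: worsening on a yes/no endpoint means no to yes; the protocol's items 4 and 5 are the SAP's Categories 4 and 5; and the subject met exclusion 6.

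The number of subjects affected is unknown and may be zero. Exclusion of a recent major depressive episode (criterion 5), recent suicidal behavior and clinically assessed suicide risk (criterion 6) may make the Category 1-3 group smaller still. No data are lost and efficacy is unaffected. A reader might take the 6 unregistered moves as a measure of size, but they describe the rule and would be the same if nobody reported ideation.

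**What to change.** Keep the four binary endpoints and the 3x3 Table 20. In SAP 10.7, before unblinding:

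- Add one row, by arm, n (%): any Category 4-5 ideation on treatment, at any time, counted whether or not behavior is also reported.
- State that a move from no ideation, or from Category 1-3, at the reference assessment to Category 4-5 on treatment counts as ideation worsening, in both the worsening count and the worsening listing.
- Leave behavior under its own endpoint. It should not form part of ideation worsening.

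The cost is one table row and one sentence. Item-level responses are already collected, and the entries will be small and mostly zeros.

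Rebuilding Table 20 with four levels is not needed. Each panel would grow from 9 to 16 cells, so the two any-time panels alone would add 2 x 3 arms x 7 = 42 cells. With every scheduled visit through Visit 13 shown as well, there would be 8 Baseline and 9 Screening panels, adding 17 x 3 x 7 = 357. If worsening were defined as moving up such a table, none to behavior would also be miscounted as ideation worsening.
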